Exposure and safety parameters

At each clinic visit, treatment exposure will be estimated with compliance rates based on patient diary cards and pill counts, and tolerability will be assessed by general enquiry and specific iron chelation tolerability questions as well as by patient diaries concerning tolerability. Study patients will receive a diary to record gastrointestinal (GI) adverse events (AEs) of special interest (AESI) during the course of the study. Patients will be given the Bristol Stool Chart with diary and instructed on its use. All AE's will be monitored throughout the trial after the first dose.

Patient safety will be monitored per clinical standard of care including routine laboratory monitoring. This will include monthly CBC, chemistry panel, and urinalysis assessments. Urine will be collected to measure protein: creatinine ratio and serum CRP will be assessed.

Compliance

Patients will be responsible for supplying their own Jadenu or Exjade during the study. Pill counts will be performed at each visit in order to characterize patient compliance (calculated as % doses taken per protocol).

Additional measures of compliance will include Investigator enquiry into patient prescription refill records if available, satisfaction with iron chelation therapy (SICT) questionnaire [ref 8; [Appendix D](#)] and use of patient diaries.

Dose reductions

Dose reductions/interruptions of DST-0509 and Jadenu/Exjade are discouraged. However, in the event of a severe or higher AE lasting for 7 or more days, the PI, at their discretion, may reduce the dose by 25-33% or interrupt dosing. The maximum interruption allowable is seven days. Dose re-escalation is not permitted. When AE resolves or is mild, the patient may restart study from last dose visit per PI or Medical Monitor (MM) discretion.

Dose suspension

Dosing with either treatment should be suspended in event of significant cytopenia (platelet count <50,000/ml or ANC <1,500/ml). If cytopenia has not recovered to Grade 1 or less after suspension of treatment for 7 days, the patient will be withdrawn from the study.

STATISTICAL ANALYSES:

A comprehensive statistical analysis plan (SAP) will be written and approved prior to database lock for this study that describes the final analyses to be completed for safety, efficacy, and pharmacokinetic endpoints.

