4.2 Exclusion Criteria

1. Patients with life expectancy less than 6 months;
2. Females of childbearing potential not on an adequate method of birth control, or who are pregnant or lactating;
3. History of non-compliance with chelation therapy (determined by the investigator, persistently taking less than 75% of prescribed dose in the 3 months prior to enrollment, or as determined by the Investigator based on medical history, SICT QoL overall score <60% or score in any SICT domain <50%);
4. Screening blood counts of the following:
 - a. Absolute neutrophil count < 1500/ μ L
 - b. Platelets < 100,000/ μ L
 - c. Hemoglobin < 8 g/dL; transfusion support is permitted;
5. Screening chemistry values of the following:
 - a. Alanine aminotransferase (ALT) and aspartate transaminase (AST) > 2.5 \times upper limit of the normal reference range (ULN)
 - b. Total bilirubin > 2 \times ULN
 - c. Creatinine > 1.5 \times ULN
 - d. Urine protein/creatinine ratio (UPCR) >0.5 mg/mg
 - e. Albumin < 2.8 g/dL;
6. History of congestive heart failure New York Heart Association (NYHA) class III or IV or uncontrolled hypertension at screening;

7. History of other malignancy within the previous 3 years, except basal cell or squamous cell carcinoma, or non-muscle invasive bladder cancer;
8. In the opinion of the Investigator, evidence of major inflammatory disease that would affect ferritin levels within 14 days prior to the start of study medication;
9. Major surgery within 30 days prior to the start of study medication;
10. Serious persistent infection within 14 days prior to the start of study medication;
11. Serious concurrent medical condition including central nervous system (CNS) disorders;
12. Requires concomitant treatment with systemic corticosteroids, or any other immunosuppressive agents, or has used such treatment in the past 10 days before study entry (use of prednisone or equivalent <10 mg/day orally or use of inhaled corticosteroids or topical steroids is permitted).
13. Previous history of difficulty swallowing oral medications;
14. Any condition that, in the opinion of the Investigator, would impair the patient's ability to comply with study procedures or study medication; or
15. Concomitant treatment with medications described in [Section 7.4](#) "Prohibited Medications".

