4.3 Patient Withdrawal Criteria

Patients may be removed from the study for reasons including the following:

1. Significant protocol violation on the part of the Investigator or patient;
2. Significant noncompliance on the part of the patient as determined by the Investigator in consultation with the Medical Monitor;
3. Patient withdraws consent;
4. During the study, patient has the need for medications, supplements, ingredients and herbal therapies that are excluded (see [Section 7.4](#), "Prohibited Medications" for examples in each category; this list is not all inclusive);
5. Unacceptable toxicity based on laboratory or other clinical findings, based on PI opinion;

6. Occurrence of any adverse event (AE) or condition that could, in the Investigator's opinion, interfere with the evaluation of the treatment effect or put the patient at undue risk;
7. Pregnancy; or
8. Other criteria, at the Investigator's discretion in consultation with the Medical Monitor.

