7.11.3 Collection, Shipment, and Retention of Laboratory Samples

All safety laboratory analyses will be performed by either a central or local laboratory. If a central laboratory is utilized, central laboratory will provide all collection materials and instructions for sample collection, packaging, and shipment. Samples for chemistry, hematology (CBC) and urinalysis will be collected at Screening and on Days 1, 14, 28, 36, 49 and 63. Samples for serum CRP will be collected at Screening and on Days 1, 28, 36, and 63.

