Dose reductions/interruptions of DST-0509 and Jadenu/Exjade are discouraged. However, in the event of a severe or higher AE lasting for >7 days, the PI, at their discretion, may reduce the dose by 25-33% or interrupt dosing. Max interruption is seven days. Dose re-escalation is not permitted. When AE resolves or is mild, the patient may restart study from last dose visit per PI or Medical Monitor (MM) discretion.

Dose suspension

Dosing with either treatment should be suspended in event of significant cytopenia – platelet count <50,000/ml or ANC <1,500/ml. If cytopenia has not recovered to Grade 1 or less after suspension of treatment for 7 days, the patient will be withdrawn from the study. The rationale for inclusion or exclusion of these subjects in the PK Population will be documented and listed.

Clinical Laboratory Parameters

Clinical laboratory measurements (serum chemistry, hematology and urinalysis) and changes from baseline will be summarized descriptively for each visit with the mean, median, standard deviation (SD), minimum and maximum, by treatment group.

Additionally, shifts from low, normal or high at baseline to low, normal or high at the end-of-treatment will be tabulated and presented by treatment group.

Vital Signs

Vital signs will be summarized descriptively for the mean, median, SD, minimum, and maximum by treatment group.

ECOG Performance Status

The ECOG performance status will be assessed at Screening Visit 1, and on Days 1, 28, 36 and 63. (see [Appendix C](#)). Changes from baseline will be presented with categorical descriptive statistics.

ECG Evaluation

ECG will be evaluated on Day 1 (Visit 3) and must be acquired predose and before blood samples are collected, and after a 5 min rest in supine position to avoid artifacts. Results will be provided in a patient listing.

Bristol Stool Chart Assessment

The Bristol Stool Chart (Section 7.13) will be used to evaluate average stool consistency: “What was the average stool consistency for the last 24 hours?” Stool Consistency will be presented with categorical description (N, % of patients) by visit for each consistency parameter: hard, lumpy, sausage, snake, soft, mushy or liquid. No formal inferential analysis will be conducted.

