4 CONTRAINDICATIONS

Exjade is contraindicated in patients with:

- Serum creatinine greater than 2 times the age-appropriate upper limit of normal or creatinine clearance less than 40 mL/min [see *Warning and Precautions (5.1)*];
- Poor performance status;
- High-risk myelodysplastic syndromes;
- Advanced malignancies;
- Platelet counts <50 x 10⁹/L;
- Known hypersensitivity to deferasirox or any component of Exjade [see *Warnings and Precautions (5.6)*, *Adverse Reactions (6.2)*].

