5.4 Bone Marrow Suppression

Neutropenia, agranulocytosis, worsening anemia, and thrombocytopenia, including fatal events, have been reported in patients treated with Exjade. Preexisting hematologic disorders may increase this risk. Monitor blood counts in all patients. Interrupt treatment with Exjade in patients who develop cytopenias until the cause of the cytopenia has been determined. Exjade is contraindicated in patients with platelet counts below $50 \times 10^9/L$.

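### The cytopenia dose-suspension thresholds are written per ml, 1000-fold below the label platelet limit and the protocol's own neutrophil entry limit

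*Protocol*

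**What the plan says.** The rule appears twice, under Dose suspension in the Synopsis and again in Section 8.5.3. Both places set the trigger for either treatment at "platelet count <50,000/ml or ANC <1,500/ml". Section 8.5.3 then adds a consequence: "If cytopenia has not recovered to Grade 1 or less after suspension of treatment for 7 days, the patient will be withdrawn" from the study.

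Elsewhere the Protocol gives the same kinds of count in other units. Section 4.2 excludes patients with "Absolute neutrophil count < 1500" per microlitre, or with platelets below 100,000 per microlitre. Section 4 of the Exjade label (Appendix A) lists "Platelet counts <50 x 10⁹/L" as a contraindication, and the Jadenu label (Appendix B) gives the same limit.

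Section 7.11.3 states that chemistry, hematology and urinalysis samples "will be collected at Screening and on Days 1, 14, 28, 36, 49 and 63".

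**The concern.** A platelet count of 50 per microlitre or a neutrophil count of 1.5 per microlitre is far below anything a safety rule would be meant to catch. A site that follows the text exactly would keep dosing a patient with severe thrombocytopenia or neutropenia.

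The withdrawal step depends on suspension having happened, so it inherits the error. The Protocol body contains no other numeric laboratory threshold for suspending dosing.

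The drug makes this relevant. Section 5.4 of both labels warns of neutropenia, agranulocytosis and thrombocytopenia, including fatal cases. Patients must enter on the maximal deferasirox dose (Section 4.1). DST-0509 is given milligram for milligram with Jadenu (Section 5.4 of the Protocol), although Section 1.2 reports better absorption than either comparator in fasted healthy volunteers.

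**Working it through.** **Inputs**

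- Suspension rule (Synopsis and Section 8.5.3): platelets 50,000 per ml; neutrophils 1,500 per ml.
- Entry limits (Section 4.2): neutrophils 1,500 per microlitre; platelets 100,000 per microlitre.
- Label platelet contraindication (Section 4 of Appendices A and B): 50 x 10⁹/L.

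**Conversions**

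- Count per microlitre = count per ml / 1000.
- Count in 10⁹/L = count per microlitre / 1000.

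**Platelets**

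- Written threshold: 50,000 / 1000 = 50 per microlitre; 50 / 1000 = 0.05 x 10⁹/L.
- Label limit: 50 x 10⁹/L = 50,000 per microlitre.
- Ratio of label limit to written threshold: 50 / 0.05 = 1000.
- Ratio of the platelet entry limit to the written threshold: 100,000 / 50 = 2000.

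**Neutrophils**

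- Written threshold: 1,500 / 1000 = 1.5 per microlitre, or 0.0015 x 10⁹/L.
- Ratio of entry limit to written threshold: 1,500 / 1.5 = 1000.

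**Counts that the written rule passes over**

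| Count per microlitre | Count per ml | Multiple of the written threshold |
|---|---|---|
| Platelets 10,000 | 10,000,000 | 10,000,000 / 50,000 = 200 |
| Neutrophils 500 | 500,000 | 500,000 / 1,500 = 333 |

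Neither patient would be suspended, although both are well inside the range that the digits suggest was intended.

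**When it would matter**

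Blood counts after the first dose fall on Days 14, 28, 36, 49 and 63.

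- Days 14, 36 and 49: the rule decides directly whether dosing goes on.
- Day 28: the washout on Days 29 to 35 stops drug anyway. A missed trigger still means that recovery is not required, and the withdrawal step is not applied, before Period 2.
- Day 63: this is the last dose, so there is no further dosing to suspend.

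**The case against.** The strongest reply is that no hematology site would apply the literal figure. The rule speaks of significant cytopenia and of recovery to Grade 1, the same sites screen patients in counts per microlitre, and the labels with the correct platelet limit are bound into the Protocol. This makes a per-microlitre reading likely. It does not make the text right: the literal and the intended readings lead to opposite actions for the same blood count, and the error stands in both statements of the rule.

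Other safeguards also remain. Section 4.3 allows withdrawal for "Unacceptable toxicity based on laboratory or other clinical findings, based on PI opinion". Section 9.1 requires the investigator to review all laboratory results and to treat a significant change from baseline as an adverse event. The Exjade label says "Interrupt treatment with Exjade in patients who develop cytopenias until the cause of the cytopenia has been determined", and the Jadenu label says the same for Jadenu. Patients are therefore not unprotected. But the Protocol routes rest on judgment, and the labels do not name DST-0509. None of them supplies the missing number.

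A misread character in the PDF text cannot be ruled out completely. It is unlikely, because the same form occurs in two separate places while the micro sign was read correctly in the exclusion criteria.

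One caution about the remedy stands. Neither label gives a numeric neutrophil limit for suspension, so the intended neutrophil value is inferred from the entry criterion alone. If it is 1,500 per microlitre, the suspension limit equals the entry limit, and a patient enrolled at that limit would be suspended on any small fall.

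**Conclusion.** The point holds. Both thresholds are too low by a factor of exactly 1000 against the label platelet limit and the neutrophil entry limit. Taken literally, the rule passes over platelets from 50 up to 50,000 per microlitre and neutrophils from 1.5 up to 1,500 per microlitre, and the withdrawal step does not start for these patients.

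This should be fixed because it is an operative safety threshold for the investigational product. It is not more serious than that: the intended values can be recovered from the document, discretionary safeguards exist, and no planned analysis uses the thresholds. The conclusion assumes that the printed page reads ml, and that the matching digits show per microlitre was meant.

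**What to change.** In the Synopsis and in Section 8.5.3, restate the trigger as platelets below 50,000 per microlitre (50 x 10⁹/L) or neutrophils below 1,500 per microlitre (1.5 x 10⁹/L). The clinical team should confirm both values, and in particular that a neutrophil suspension limit equal to the entry limit is intended.

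Two editorial points can go into the same edit; neither adds to the weight of this one. The Synopsis allows dose reduction "in the event of a severe or higher AE lasting for 7 or more days", while Section 8.5.3 requires more than 7 days, so one duration should be chosen. Severe is also the top grade in Section 9.3, so the reference to anything higher should go.

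The cost is a short amendment or a clarification letter to sites, with no added visits, procedures or data.

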8.5.4 Pharmacokinetic Analyses

8.5.4.1 Pharmacokinetic Parameters

Blood samples for PK analysis will be collected predose (-0.5 hour) and at 1, 2, 4, and 8 hours postdose on Days 1, 7, 28, 36, 42 and 63. The PK parameters of DST-0509 and Jadenu and Exjade will be derived from the concentration-time data. The allowed sampling “window” is ± 15 min for the 1 and 2 hour time points, and ± 30 min for the 4 hour time point. For the 8 hour time point, the allowable window is ± 1 hour.

Total (iron-bound and unbound) DFX plasma concentrations produced by the administration of the studied formulations (DST-0509 and Jadenu/Exjade) will be determined in order to establish the pharmacokinetic profile of each treatment.

Pharmacokinetic parameter estimates will be estimated for each treatment. Both single dose PK parameter estimates (following the first dose in a treatment sequence) and multiple dose PK parameter estimates will be completed to characterize DST-0509 and Jadenu/Exjade. The following parameters will be estimated for this study for each treatment:

Table 8-1. PHARMACOKINETIC PARAMETERS

Pharmacokinetic Parameter	Description (Computation Method)
Following first dose in each treatment sequence:	
C_{max}	Peak exposure, Maximum plasma concentration.
t_{max}	Time to maximum plasma concentration.
C_{last}	Last quantifiable plasma concentration (last value observed above assay BLQ).
t_{last}	Time of last quantifiable plasma concentration.
λ_z	Terminal rate constant (lambda_z).
$t_{1/2}$	Terminal half-life: Computed as $t_{1/2} = \frac{\ln(2)}{\lambda_z}$
$AUC_{(0-t)}$	Exposure: Area Under the Plasma Curve from time 0 to the last quantifiable concentration (t). Calculated using the linear trapezoidal rule.
$AUC_{(0-24)}$	Exposure: Area Under the Plasma Curve from time 0 to 24 hours post dosing. Calculated using the linear trapezoidal rule.
$AUC_{(0-\infty)}$	Exposure: Area Under the Plasma Curve from time 0 extrapolated to infinity. Calculated as follows: $AUC_{inf} = AUC_{0-t} + \left(\frac{C_{last}}{\lambda_z} \right)$ where C_{last} is the last quantifiable concentration.
CL/F	Apparent oral clearance, computed as Dose / $AUC_{(0-\infty)}$
$AUMC_{(0-\infty)}$	Area under the first moment curve extrapolated to infinity, computed as: $AUMC_{last} + \frac{T_{last} \cdot C_{last_{obs}}}{\lambda_z} + \frac{C_{last_{obs}}}{\lambda_z^2}$
MRT	Mean residence time based on concentration-time data extrapolated to infinity, computed as $AUMC_{(0-\infty)} / AUC_{(0-\infty)}$
Multiple dose pharmacokinetic parameters within each sequence:	
Tau	The (assumed equal) dosing interval for steady-state data.
T_{max}	Time of maximum concentration sampled during a dosing interval.
T_{min}	Time of minimum concentration sampled during a dosing interval.
C_{min}	Minimum concentration between dose time and dose time + Tau (at T_{min}).
C_{avg}	Average concentration over the dosing interval, computed as AUC_{0-tau}/tau .
%_Fluctuation	$100 \cdot (C_{max} - C_{min}) / C_{avg}$, for C_{min} and C_{max} between dose time and Tau.
Cl_{ss}/F	An estimate of apparent oral clearance after multiple dosing, computed as Dose/ AUC_{0-tau} .
C_{max}	Maximum concentration between dose time and dose time + Tau (at T_{max}).
AUC_{0-tau}	Area Under the Plasma Concentration curve from the time of the dose to the end of the dosing interval.

Additional PK parameters may be derived as need to characterize both single dose and multiple dose PK profiles.

All reported sampling time deviations will be taken into consideration for evaluation of PK parameters. In the case where concentrations of study medications cannot be determined due to bioanalytical or clinical reasons; these values will be set to missing for the statistical and pharmacokinetic analysis.

The main absorption and disposition parameters will be estimated using a non-compartmental approach with a log-linear terminal phase assumption. The trapezoidal rule will be used to estimate the area under the curve (linear trapezoidal linear interpolation) and the terminal phase will be estimated by maximizing the coefficient of determination estimated from the log-linear regression model. However, disposition parameters may be estimated for individual concentration-time profiles on Day 1 where the terminal log-linear phase cannot be reliably characterized. Descriptive statistics will be calculated for plasma concentrations at each individual time point and for all pharmacokinetic parameters. The individual plasma concentration/time profiles will be presented using the actual sampling times whereas the mean plasma concentration/time profiles will be presented using the theoretical sampling times.

Pharmacokinetic parameters will be derived using model-independent methods (non-compartmental analysis: NCA) as implemented in Phoenix 7, WinNonlin (version 7.1) and will be based on DST-0509 and Jadenu plasma concentrations from patients in the PK Population.

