DST-0509 is manufactured using a thermokinetic mixing process, or fusion process to produce drug-polymer composites, and specifically an amorphous drug-polymer intermediate. The process has been repeatedly demonstrated in the pharmaceutical literature to produce amorphous drug-polymer intermediates with compounds that could not be successfully melt-extruded owing to their high melting points. The composition provides improved DFX solubility and dissolution properties that may result in enhanced bioavailability and reduced pharmacokinetic variability in patients. These attributes are expected to translate into less variability in response, and improved efficacy in non-responders as compared to existing marketed DFX products.

The FDA approved initial dose of Exjade is 20 mg/kg and may be titrated up to 40 mg/kg [1]. The dosing of Jadenu is initially 7 or 14 mg per kg body weight (depending on the indication) orally, once daily [2]. The maximum recommended dosage of Jadenu is 28 mg per kg body weight orally, once daily [2]. Galanello, et al reported that ICL670 (Exjade) was well tolerated, and no safety problems occurred up to 80 mg/kg following administration of a single dose [4].

DFX is absorbed following oral administration with median times to maximum plasma concentration (T_{max}) of about 1.5 to 4 hours. The C_{max} and AUC of DFX increase approximately linearly after both single administration and under steady-state conditions. Exposure to DFX increased by an accumulation factor of 1.3-2.3 after multiple doses. The absolute bioavailability (AUC) of DFX tablets for oral suspension is 70% compared to an intravenous dose. The bioavailability (AUC) of DFX was variably increased when taken with a meal [1,2].

DFX is highly (~99%) protein bound almost exclusively to serum albumin. The percentage of DFX confined to the blood cells was 5% in humans. The volume of distribution at steady-state of DFX is 14.37 ± 2.69 L in adults. Glucuronidation is the main metabolic pathway for DFX, with subsequent biliary excretion.

DFX and metabolites are primarily (84% of the dose) excreted in the feces. Renal excretion of DFX and metabolites is minimal (8% of the administered dose). The mean elimination half-life ($t_{1/2}$) ranged from 8-16 hours following oral administration [1,2]

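### PK sampling stops at 8 h, but Table 8-1 plans AUC0-24, AUC0-inf, half-life, CL/F and AUC0-tau with no rule for 8 to 24 h

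*Protocol*

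**What the plan says.** - **Sampling (Section 8.5.4.1):** blood is "collected predose (-0.5 hour) and at 1, 2, 4, and 8 hours postdose on Days 1, 7, 28, 36, 42 and 63". The last point may move: "For the 8 hour time point, the allowable window is ± 1 hour". There is no 24 h sample.
- **First-dose list (Table 8-1):** lambda_z, half-life, AUC0-t, AUC0-24, AUC0-inf, CL/F, AUMC0-inf and MRT. AUC0-24 is "Area Under the Plasma Curve from time 0 to 24 hours post dosing. Calculated using the linear trapezoidal rule".
- **Multiple-dose list (Table 8-1):** AUC0-tau, defined as "Area Under the Plasma Concentration curve from the time of the dose to the end of the dosing interval", with Cavg, fluctuation and CLss/F derived from it. Dosing is once daily, so tau is 24 h. No closing rule is given.
- **Terminal slope (text after Table 8-1):** "the terminal phase will be estimated by maximizing the coefficient of determination estimated from the log-linear regression model". The next sentence opens with *However* and says that "disposition parameters may be estimated for individual concentration-time profiles on Day 1 where the terminal log-linear phase cannot be reliably characterized".
- **Disposition (Section 1.1):** mean half-life "ranged from 8-16 hours following oral administration"; median Tmax about 1.5 to 4 h.
- **Comparison (Section 8.5.4.2):** Cmax and AUC enter an ANOVA with 90% confidence intervals. Which AUC is meant is not stated.
- **Exclusion (Section 8.3):** a patient whose predose concentration exceeds 5% of that period's Cmax is dropped from all PK and statistical evaluations. The rule is not limited to first-dose days.

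**The concern.** The last sample falls between half a half-life (8/16) and one half-life (8/8) after dosing. A linear trapezoid to 24 h has no later concentration to join to, so the stated method for AUC0-24 cannot be carried out. AUC0-inf, CL/F, AUMC and MRT depend on a slope fitted to a short stretch close to the peak.

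The Synopsis states the PK goal as comparing exposure on current therapy with exposure on DST-0509 after 4 weeks. The only AUC that Table 8-1 lists for that setting is AUC0-tau, and nothing says how to obtain it from samples ending at 8 h.

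A slope read this early also carries residual absorption. Two treatments with the same true exposure but different absorption rates could then show different estimated AUC0-inf. The trial compares formulations and allows different food conditions (Section 5.4), so this could affect a treatment ratio if AUC0-inf or AUC0-24 were the AUC analysed.

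The Day 1 sentence, as printed, permits disposition parameters exactly where they cannot be trusted.

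**Working it through.** The protocol gives no extrapolated share, so there is no stated figure to reproduce. The shares below are modelled.

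**Inputs.** Half-life 8, 12, 16 h and Tmax 1.5-4 h (Section 1.1); samples at 0, 1, 2, 4, 8 h and the parameter definitions (Section 8.5.4.1); tau 24 h (once daily, Section 3.1). *Assumptions:* one compartment, first-order absorption with ka 0.6, 1 or 2 per h, dose/volume set to 1.

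**Formulas.** k = ln 2 / half-life.
- C(t) = ka/(ka-k) × (e^(-kt) - e^(-ka·t))
- AUC(0-T) = ka/(ka-k) × [(1-e^(-kT))/k - (1-e^(-ka·T))/ka]
- AUC0-inf = 1/k
- Estimated AUC0-inf = trapezoid(0-8) + C(8)/λ, with λ = ln(C4/C8)/4

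**One case in full (half-life 12 h, ka 1).** k = 0.0578. AUC0-8 = 5.74 and AUC0-inf = 17.31, so 1 - 5.74/17.31 = 67% lies beyond 8 h. C4 = 0.823 and C8 = 0.668, so λ = ln(0.823/0.668)/4 = 0.0521, an apparent half-life of 13.3 h. The trapezoid gives 5.62. Then 5.62 + 0.668/0.0521 = 18.45, which is 1.07 times the true value.

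**All cases.** Percentages are the share of the true AUC beyond 8 h.

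| Half-life (h) | ka (/h) | Tmax (h) | AUC0-24 | AUC0-tau (steady state) | AUC0-inf | Estimated/true AUC0-inf (4-8 h slope) |
|---|---|---|---|---|---|---|
| 8 | 0.6 | 3.8 | 51% | 50% | 58% | 1.29 |
| 8 | 1 | 2.7 | 48% | 47% | 55% | 1.03 |
| 8 | 2 | 1.6 | 45% | 45% | 52% | 0.99 |
| 12 | 0.6 | 4.3* | 58% | 56% | 70% | 1.59* |
| 12 | 1 | 3.0 | 55% | 54% | 67% | 1.07 |
| 12 | 2 | 1.8 | 53% | 52% | 65% | 0.99 |
| 16 | 0.6 | 4.7* | 61% | 59% | 76% | 2.08* |
| 16 | 1 | 3.3 | 59% | 57% | 74% | 1.10 |
| 16 | 2 | 2.0 | 57% | 56% | 72% | 0.99 |

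*Tmax outside the documented 1.5-4 h.

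**Other fitting rule.** With λ from the 2, 4 and 8 h points and ka solved from Tmax, estimated/true AUC0-inf is 1.00-1.05 at Tmax 1.5-2 h, 1.40-1.50 at 3 h and 4.4-11.8 at 4 h.

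**Noise.** With an assumed 10% log-normal error, the same three-point fit and Tmax 2-3 h, the geometric CV is about 5-6% for AUC0-t and 28-102% for AUC0-inf. Between 0% and 13% of profiles give no positive slope.

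**Closing AUC0-tau with the predose value as the 24 h value.** By Day 7, six days (144 h) of dosing span 144/16 = 9 to 144/8 = 18 half-lives, so steady state is reasonable. Over the nine cases the linear rule is 1.5-6.4% high, and linear-up/log-down is 0.6-1.5% low.

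**Section 8.3 rule.** Modelled steady-state predose is 15-45% of Cmax, at least three times the 5% limit. After a 7-day washout, 168/16 = 10.5 half-lives or more have passed, so on Days 1 and 36 the rule is a sensible carry-over check.

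**The case against.** Several points on the other side stand.

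- **Not every exposure measure is affected.** Cmax and AUC0-t use observed data only. A reader might infer that the treatment ratios as a whole rest mainly on extrapolation. Section 8.5.4.2 does not name its AUC, so the protocol does not support that. For AUC0-24 and AUC0-tau the part beyond 8 h is roughly half; it is a majority throughout only for AUC0-inf and what derives from it.
- **The Day 1 sentence permits; it does not instruct.** It says *may*, for disposition parameters, on Day 1. A lost *not* is likely given the opening *However*, but that is an inference.
- **The largest biases are out of range.** The +59% and +108% cases need a Tmax of 4.3 and 4.7 h. In range, the 4-8 h slope gives +3% to +10% at ka 1, and only the +29% case is large.
- **The slope need not rest on two points.** With Tmax at 1.5 h the 2 h sample is past the peak, and the three-point fit is then close to the truth. Nothing says that two-point fits are allowed.
- **A differential bias is hypothetical.** The protocol gives no absorption rate or Tmax for DST-0509.
- **Detail may sit in the SAP.** Section 8 leaves full PK detail there, and a predose closing rule is not forbidden. But the protocol itself names a trapezoid to 24 h that its schedule cannot supply, and Section 8.3 as written conflicts with that closing rule.

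**Conclusion.** The concern holds as a mismatch between the sampling schedule and the listed parameters. First-dose AUC0-24 cannot be computed by the stated rule. AUC0-inf, half-life, CL/F, AUMC and MRT are weakly supported by samples that end within one half-life of dosing. AUC0-tau, Cavg and CLss/F have no rule for 8-24 h.

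In the model, about 45-61% of AUC0-24 or AUC0-tau and 52-76% of AUC0-inf lie beyond 8 h. Within the documented Tmax range, AUC0-inf from the 4-8 h slope runs from about -1% to +29% of the truth, and further under other fitting rules. The figures assume one compartment, first-order absorption and that the cited deferasirox half-life and Tmax apply to every formulation. Enterohepatic recycling (Section 7.4) is ignored and would tend to raise late exposure.

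This should be fixed, but it does not undermine the trial: PK is a secondary objective (Section 2.2), and the sample size rests on diarrhea events (Section 8.1).

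**What to change.** 1. **Days 7, 28, 42, 63:** close AUC0-tau with that day's predose concentration as the 24 h value, using linear-up/log-down integration. Name AUC0-tau and Cmax on Days 28 and 63 as the exposure parameters in the Section 8.5.4.2 ANOVA.
2. **Days 1 and 36:** compare Cmax and AUC0-8 only, with AUC cut at a fixed 8 h because the last sample may fall at 7 to 9 h. Remove AUC0-24, AUC0-inf, half-life, CL/F, AUMC and MRT from the first-dose list. Keeping them under a cap on the extrapolated share would achieve little: at least 52% of AUC0-inf lies beyond 8 h in every modelled case.
3. **Section 8.3:** limit the exclusion for predose above 5% of Cmax to Days 1 and 36. Otherwise it would remove nearly every patient at steady state and defeat item 1.
4. **Section 8.5.4.1:** correct the Day 1 sentence so that disposition parameters may *not* be estimated where the terminal phase cannot be reliably characterized.

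The cost is wording in Table 8-1, Sections 8.3, 8.5.4.1 and 8.5.4.2, and the SAP. No samples or visits are added. The price is that no half-life or single-dose clearance is reported. Item 1 also assumes that the previous dose was taken about 24 h before the visit dose, so its time should be recorded.
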